4.8.6. Removal of Subjects from Investigational Product

A subject may discontinue from receiving the IP for any of the following reasons:

- Occurrence of any medical condition or circumstance that, in the opinion of the Investigator, exposes the subject to substantial risk and/or does not allow the subject to adhere to the requirements for IP administration as per the Protocol.
- Occurrence of or considerable worsening of an AE (described in [Section 5.7](#)) that, in the opinion of the Investigator in consultation with the Medical Monitor and Sponsor, represents an unacceptable risk to the subject if he/she continues in the study. The Investigator must follow the subject until the AE resolves or satisfactorily stabilizes.

- IP application must be discontinued immediately in the event of a female subject's pregnancy.
- Subject's decision to withdraw from receiving IP.
- Weight loss of >5% from Baseline, if not dieting or intentionally trying to lose weight, at the Investigator's discretion and after consultation with the Medical Monitor and Sponsor.
- C-SSRS indicative of suicidal ideation
- PHQ-8/PHQ-A score ≥ 15 if determined by Investigator in consultation with a mental health professional.
- Requirement for use of prohibited concomitant medication ([Table 1](#)) after consultation with the Sponsor and Medical Monitor.
- Subjects repeated failure to comply with protocol requirements or study related procedures.

4.8.7. Removal of Subjects from the Study

A subject may be removed from study participation for any of the following reasons:

- Subject's decision to withdraw from the study.
- Subject's death.
- Subject is lost to follow-up. A subject will be considered lost to follow-up after three phone and three email attempts and documentation of a certified letter sent to the subject's address.
- Termination of the study by the Sponsor, FDA, or other regulatory authorities.

5. STUDY PROCEDURES

The Schedule of Visits and Assessments ([Section 1.3](#)) summarizes the clinical procedures to be performed at each visit. Individual clinical procedures are described in detail below. Additional evaluations/testing may be deemed necessary by the Investigator and/or the Sponsor for reasons related to subject safety.

5.1. Safety Assessments

This study assesses the safety and efficacy of ARQ-154 foam 0.3%. Safety will be determined by evaluating physical examinations, vital signs/weight, local tolerability assessments, clinical laboratory parameters, PHQ-8/PHQ-A, C-SSRS, and AEs as outlined in the Schedule of Visits and Assessments ([Section 1.3](#)). If deemed necessary, additional safety assessments will be performed at the discretion of the Investigator.

5.1.1. Screening

Before a subject's participation in the clinical study, the Investigator is responsible for obtaining written informed consent from the subject or written assent from adolescent subjects and consent from their parent(s) or legal guardian(s) after adequate explanation of the study design, anticipated benefits, and the potential risks. Informed consent must be obtained before completion of any non-standard of care study-specific procedures. Procedures that are part of standard of care are not considered study-specific and, therefore, may be performed prior to obtaining consent and used to confirm eligibility provided they occur within the time allowance outlined in the Schedule of Visits and Assessments ([Section 1.3](#)). A subject is considered a participant of the study once the informed consent form (ICF) (and written assent for an adolescent subject) is completely signed.

The following procedures/assessments will be performed at the Screening Visit (within 4 weeks after signing the ICF/assent):

- Review of medical and surgical history
- Review of childbearing potential (female subjects) and contraceptive use ([Section 5.1.2](#))
- Collection of demographic data including age, sex, race, ethnicity
- Limited physical examination of skin (including assessment of Fitzpatrick Skin Type at Screening only), lungs, heart
- Vitals signs including temperature, heart rate, blood pressure
- Collection of height (cm) and body weight (kg)
- Laboratory tests: hematology, chemistry, urinalysis, serum pregnancy (for female subjects of childbearing potential) and FSH (to confirm post-menopausal status)
- Scalp and body psoriasis assessments: S-IGA, B-IGA, PSSI, BSA, PASI
- Completion of DLQI/CDLQI, Scalpdex, PSD
- C-SSRS, PHQ-8/PHQ-A
- Collection of prior and concomitant medication

All screened subjects will receive a subject identification number (see [Section 4.4](#)) and be entered into the eCRF. Subjects that fail to meet the eligibility criteria will be designated as a screen failure and entered in the IWRS and eCRF as such. Subjects who are unable to enroll within the screening window will be rescreened.

[figure not shown]
Subjects may be re-screened one time. The original assigned subject ID number will be used for re-screening.

Subjects who consent but do not proceed with enrollment will be considered a screen fail.

5.1.2. Contraception Requirements

Females of childbearing potential (FOCBP) must have a negative serum pregnancy test at Screening (Visit 1) and a negative urine pregnancy test at Baseline (Visit 2), Week 4 (Visit 4) and Week 8 (Visit 5). In addition, sexually active FOCBP must agree to use at least one form of a highly effective or barrier method of contraception throughout the study according to Contraception Requirements for Female Subjects. Prepubescent females must agree to be abstinent during the entire course of the study (Figure 1).

Figure 1: Contraception Requirements for Female Subjects

¹Subjects using hormonal contraceptives must have been on a stable dose for at least 4 weeks before Day 1.

²The above list of contraceptive methods does not apply to subjects who are abstinent for at least 4 weeks before Day 1 and will continue to be abstinent from penile-vaginal intercourse throughout the study. The reliability of sexual abstinence needs to be evaluated in relation to the duration of the clinical trial and the preferred and usual lifestyle of the participant.

³Female condom and male condom should not be used together.

5.1.3. Baseline

Each subject will undergo Baseline assessments outline in the Schedule of Visits and Assessments (Section 1.3). For subjects <18 years, if the Baseline (Day 1) visit occurs within 3 weeks of Screening, the Screening lab results may be utilized.

Randomization and IP kit assignment will take place via IWRS after the subject has been found to be fully eligible for participation. A subject will be considered enrolled into the study upon the first IP application.

5.1.4. Physical Examination

Physical examinations will be performed according to the Schedule of Visits and Assessments (Section 1.3). The physical exam will be limited to skin (including assessment of Fitzpatrick skin type at Screening only), lungs, and heart only.

Fitzpatrick skin phototype assessment will be rated as follows:

- I. Always burns easily; never tans (sensitive)
- II. Always burns easily; tans minimally (sensitive)
- III. Burns moderately; tans gradually (light brown) (normal)
- IV. Burns minimally; always tans well (moderate brown) (normal)
- V. Rarely burns; tans profusely (dark brown) (insensitive)
- VI. Never burns; deeply pigmented (insensitive)

5.1.5. Vital Signs, Height and Weight

Vital signs will be performed according to the Schedule of Visits and Assessments ([Section 1.3](#)).

Blood pressure, heart rate, and temperature will be measured while the subject is sitting/resting for at least 5 minutes.

Height will be collected at Screening and Week 8.

Subjects should void prior to weight being taken and remove any objects of significant weight (i.e., jackets, outerwear, shoes, cell phones, wallet, key chains, etc.). A 5% unintentional weight loss from Baseline should be reported to the medical monitor.

5.1.6. Laboratory Tests

All tests listed in [Table 2](#) will be performed according to the Schedule of Visits and Assessments ([Section 1.3](#)) unless otherwise noted. For subjects <18 years old, Screening safety lab results collected within 3 weeks of the Baseline visit may be utilized as the Baseline safety lab assessment. No food restrictions are required for the collection of specimens. In addition, laboratory safety tests may be performed at unscheduled time points, if deemed necessary by the Investigator. Laboratory samples will be sent to the central lab. Refer to the most current Central Laboratory Manual for collection, processing, shipping, and report receipt instructions.

Table 2: Laboratory Tests

Hematology	Serum Chemistry

• Hemoglobin• Hematocrit• Total and differential leukocyte count• Red blood cell count with indices and morphology• Platelet count	
• Blood Urea Nitrogen• Bilirubin (total and direct)• Alkaline phosphatase• Aspartate aminotransferase• Alanine aminotransferase• Albumin• Sodium• Potassium• Chloride• Glucose• Creatinine

Table 2: Laboratory Tests (Continued)

Urinalysis	Additional Tests

• pH• Specific gravity• Protein*• Glucose• Ketones• Bilirubin• Blood*• Nitrite*• Urobilinogen• Leukocyte esterase*	
• Urine pregnancy test**• (for females of childbearing potential only)• Serum pregnancy test (hCG)***• FSH****• Pharmacokinetic (PK) assessments

*If urinalysis is positive for protein, blood, nitrite and/or leukocyte esterase, a microscopic examination (for red blood cells, white blood cells, bacteria, casts, and epithelial cells) will be performed.

** Baseline, Weeks 4, and 8, for FOCBP only

*** At Screening, for FOCBP only

****At Screening, for postmenopausal females only

5.1.7. Patient Health Questionnaire Depression Scale (PHQ-8)

The PHQ-8 Assessment (see [Appendix 2](#)) will be completed by adult subjects according to the Schedule of Visits and Assessments ([Section 1.3](#)).

PHQ-8 score is the sum of the responses for the 8 questions.

Five severity categories of depression are defined as follows:

- None – Minimal depression (1 to 4)
- Mild depression (5 to 9)
- Moderate depression (10 to 14)
- Moderately severe depression (15 to 19)
- Severe depression (20 to 24)

Subjects with a PHQ-8 score of 10-14 should be referred to a mental health professional for evaluation, regardless of the reason for their change in score.

Subjects with a PHQ-8 score of ≥ 15 should be immediately referred to a mental healthcare professional and Investigators in consultation with the mental health professional should consider interruption or discontinuation of the investigational product.

5.1.8. Patient Health Questionnaire Depression Scale (Modified PHQ-A)

The Modified PHQ-A Assessment ([Appendix 3](#)) will be completed by adolescent subjects (12-17 years old, inclusive) according to the Schedule of Visits and Assessments ([Section 1.3](#)).

Modified PHQ-A score is the sum of the responses for the 8 questions.

Five severity categories of depression are defined as follows:

- None - Minimal depression (0 to 4)
- Mild depression (5 to 9)
- Moderate depression (10 to 14)
- Moderately severe depression (15 to 19)
- Severe depression (20 to 24)

Subjects with a modified PHQ-A score of 10-14 should be referred to a mental health professional for evaluation, regardless of the reason for their change in score.

Subjects with a modified PHQ-A score ≥ 15 should be immediately referred to a mental health professional, and Investigators in consultation with the mental health professional should consider interruption or discontinuation of the investigational product.

5.1.9. Columbia-Suicide Severity Rating Scale (C-SSRS)

C-SSRS Assessments will be performed according to the Schedule of Visits and Assessments ([Section 1.3](#)).

The administration schedule of the C-SSRS will be:

- The Baseline-Screening version ([Appendix 4](#)) will be used at Screening to provide a pre-treatment assessment Baseline. The timeframe for the Baseline-Screening version is the past 6 months for suicidal ideation and past 5 years for suicidal behavior.
- On all subsequent visits, the Since Last Visit version ([Appendix 5](#)) will be used.
- A score greater than 0 at the Screening or Baseline visit in suicidal ideation may indicate the need for mental health intervention. The Investigator should not enroll the subject in the study.
- Any score greater than 0 in the suicidal ideation score may indicate the need for mental health intervention. The Investigator should give consideration for the subject to discontinue from the IP and prompt referral to a mental health professional and/or possibly the emergency room. The Medical Monitor should be contacted.

The C-SSRS administrator will be trained via C-SSRS training video. A training certificate for the administrator(s) will be on file in the trial master file at the site.

The Investigator must review the completed C-SSRS. A qualified mental health care provider must be available, immediately if needed, to refer the subject for further evaluation.

5.1.10. Local Tolerability Assessment

The Investigator Local Tolerability Assessment will be performed according to the Schedule of Visits and Assessments ([Section 1.3](#)).

Application site reasons will be graded at each timepoint. Irritation reactions are graded using the scale detailed in the following section ([Berger 1982](#)). **Reactions at the site of product application, which may occur post-Baseline, should be differentiated from the preexisting inflammation associated with the subject's psoriasis.**

For the Baseline, Weeks 2, 4 and 8 visits, when IP is applied in the clinic, the Investigator assessments will be conducted by the Investigator prior to IP application.

Dermal Response

- 0 = no evidence of irritation
- 1 = minimal erythema, barely perceptible
- 2 = definite erythema, readily visible; minimal edema or minimal papular response
- 3 = erythema and papules
- 4 = definite erythema
- 5 = erythema, edema and papules
- 6 = vesicular eruption
- 7 = strong reaction spreading beyond application site

The Subject Local Tolerability Assessment will be performed according to the Schedule of Visits and Assessments ([Section 1.3](#)).

This assessment will be administered by the site 10 to 15 minutes after IP application in the clinic at Baseline and Weeks 2 and 4, and a recall assessment at Week 8.

Grade	Sensation Following Investigational Product Application
0 (none)	No sensation
1 (mild)	Slight warm, tingling sensation; not really bothersome
2 (moderate)	Definite warm, tingling sensation that is somewhat bothersome
3 (severe)	Hot, tingling/stinging sensation that has caused definite discomfort

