5.9. Treatment Stopping Rules

If a subject has non-cutaneous adverse events of concern, clinically significant laboratory values or any condition that the Investigator determines could possibly be related to the investigational product, the Investigator should immediately contact the Medical Monitor to discuss if the subject should be discontinued from treatment with investigational product.

Treatment for any individual subject will be discontinued if the subject experiences:

- A SAE or a clinically significant non-serious AE which in the opinion of the Principal Investigator or Medical Monitor warrants discontinuation from the study for that subject's well-being
- A treatment-emergent severe (Grade 3) laboratory abnormality (confirmed by repeat sample) which in the opinion of the Principal Investigator or Medical Monitor warrants discontinuation from the study for that subject's well-being

A subject with a PHQ-8/PHQ-A score ≥ 15 should receive immediate referral to a mental health care professional, and Investigators in consultation with the mental health professional should consider interruption or discontinuation of the investigational product.

- Subjects with a PHQ-8 or modified PHQ-A score of 10-14 should be referred to a mental health professional for evaluation, regardless of the reason for their change in score

A subject that is experiencing suicidal ideation and behavior should be referred immediately to a qualified mental health care provider and consideration given to discontinuation from IP.

As noted above, IP must be discontinued immediately in the event of a female subject's pregnancy.

IP Treatment should be interrupted:

- If a subject develops an application site reaction with the clinical appearance of an 'irritation reaction', and with a severity of a Dermal Response Score of 5 (erythema, edema, and papules) or greater on the scale of Berger and Bowman, treatment should be interrupted for up to one week and may then be resumed if the reaction has, in the opinion of the Investigator, adequately resolved.

IP Treatment should be discontinued:

- If the reaction reoccurs. IP should be discontinued permanently, and the subject followed until the reaction resolves.

For cases of suspected allergic contact dermatitis, the medical monitor and sponsor should be notified and there should be discussion about performing patch testing to further evaluate. Patch testing is encouraged in such cases.

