- d. Height will be collected at Screening and Week 8. Weight will be collected at all study visits. Subjects should void prior to weight being taken and remove any objects of significant weight (i.e., jackets, outerwear, shoes, cell phones, wallet, key chains, etc.). A 5% unintentional weight loss from Baseline should be reported to the medical monitor.
- e. S-IGA will be a 5-point scale ranging from clear (0) to severe (4) and is evaluated for the scalp only. B-IGA will use the same scale as S-IGA but will evaluate the entire body (except the scalp, palms, and soles). PSSI is scored on a 0-72 scale and evaluates the scalp only. PASI assessment should exclude palms and soles. **S-IGA and B-IGA should be completed prior to other Investigator assessments and every effort should be made for the same evaluator to complete at each study visit.**
- f. Total BSA affected by scalp and body psoriasis will be determined by the subject's hand method, where the subject's hand (including fingers) surface area is assumed to equal 1% of body surface area. Scalp will be included in total BSA measurement, but palms and soles will be excluded. The total scalp (ie, 100% of the total scalp surface area) can be considered to be approximately 4% BSA.
- g. Extent of scalp involvement will be the extent of psoriasis involved, expressed as a percentage of total scalp.
- h. The DLQI will be completed by subjects ≥ 17 years of age. The CDLQI will be completed for subjects 12 to 16 years old, inclusive. Scalpdex will be completed by all subjects. PSD will be completed by subjects ≥ 18 years of age.
- i. Subjects/parents/caregivers will complete the SI-NRS and WI-NRS daily at home starting 7 days prior to the Baseline/Day 1 visit to Day 57 (Week 8) visit. Daily SI-NRS and WI-NRS will be completed in the evening prior to IP application (except at Baseline and Week 2 when IP is applied at the clinic). **The SI-NRS should be completed first and then WI-NRS.**
- j. Local tolerability assessments include both investigator and subject assessments. The Investigator assessment of skin irritation (Berger and Bowman skin irritation score) is to be recorded prior to IP application.

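### Grade 4 of the dermal response scale in protocol 5.1.10 is not a step above grade 3, so grades 2 to 4 are not in order of severity (minor)

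*Protocol*

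**What the plan says.** Protocol 5.1.10 makes the printed list the working instrument: "Irritation reactions are graded using the scale detailed in the following section". Four consecutive anchors matter here:

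- "2 = definite erythema, readily visible; minimal edema or minimal papular response"
- "3 = erythema and papules"
- "4 = definite erythema"
- "5 = erythema, edema and papules"

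The investigator rates the skin at Baseline and Weeks 2, 4 and 8, each time before any product is applied in the clinic.

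Protocol 5.9 uses the same score. It interrupts treatment for an irritation reaction "with a severity of a Dermal Response Score of 5 (erythema, edema, and papules) or greater", and on recurrence it adds: "If the reaction reoccurs. IP should be discontinued permanently".

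Protocol 6.2.4 and SAP 9.2 summarise the score by visit in two ways, as counts and percentages and as means and medians. The outputs are SAP Tables 14.3.2.2 (categorical) and 14.3.2.1 (quantitative). "The Investigator assessment of skin irritation" also appears in SAP Table 1, footnote j, which names the published scale but does not restate its grades.

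**The concern.** An ordinal scale works only if each grade describes something worse than the grade below it. Here grade 4 adds nothing to grade 2 and names less than grade 3, while grade 5 suddenly requires three signs together. A rater who follows the text has no clear instruction for plain definite erythema, and no grade at all for erythema with more than minimal edema and no papules.

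Local tolerability is a listed safety endpoint (SAP 2.2.1), and safety is part of the primary objective (protocol 3.1.1). For a product applied to the skin, the irritation tables are read closely. If the grades are out of order, counts at the affected grades cannot be read as a severity gradient. A mean or median that treats 4 as worse than 3 and 2 has no clear meaning in that range.

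**Working it through.** No arithmetic is at issue, so the check sets the printed anchors side by side.

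**Signs named at each grade (protocol 5.1.10)**

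| Grade | Erythema | Edema | Papules |
|---|---|---|---|
| 2 | definite | minimal (or minimal papules) | minimal (or minimal edema) |
| 3 | yes | not named | yes |
| 4 | definite | not named | not named |
| 5 | yes | yes | yes |

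Grade 6 is defined by vesicles, and grade 7 by a strong reaction that spreads past the application site.

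**Step 1: grade 4 against grades 2 and 3.** The only qualifier at grade 4 is the word definite, which grade 2 already uses. Grade 2 can be read in two ways:

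- *Edema or papules optional at grade 2.* Definite erythema alone then fits both 2 and 4. The same skin can be scored 4 − 2 = 2 points apart on a 0 to 7 scale.
- *Edema or papules required at grade 2.* Definite erythema alone then fits only grade 4, and so ranks above erythema with papules at grade 3.

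On either reading, grades 2 to 4 are not in increasing order.

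**Step 2: the uncovered presentation.** Take erythema with more than minimal edema and no papules, vesicles or spread. It exceeds grade 2, which allows only minimal edema. It lacks the papules that grades 3 and 5 name. It has edema, which grade 4 does not name. It lacks the features that define grades 6 and 7. No printed grade describes it.

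**Step 3: is the anchor defined elsewhere?** Protocol 5.9 repeats only the grade 5 wording. SAP footnote j gives only the name of the scale. Neither document gives a second definition of grade 4.

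**Step 4: the interruption threshold.** A score of 5 needs erythema, edema and papules together, and 5.9 repeats that inside the rule. The presentation in Step 2 does not meet it, and nothing in its description meets 6 or 7. It therefore falls below the threshold. What is undefined is which lower number it should receive.

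**Step 5: reach.** Grades 0 to 7 give 8 anchors, of which 1 is faulty. The Baseline rating precedes any product, so treatment-related scores can arise at 4 − 1 = 3 scheduled visits (Weeks 2, 4 and 8). Two planned tables use the score.

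**The case against.** The strongest case on the other side is that this is a one-line wording error with no shown effect. Protocol 5.9 and SAP footnote j name a published scale, and raters or the eCRF may have carried its proper text. SAP section 9 excludes inferential safety tests. SAP 9.2 reports the number at each score, so any grade 4 ratings stay visible and are not buried in a mean. If nobody was rated 4 and no reaction showed edema without papules, no table changes. A rater might also place such a reaction at 4 simply by position. The point also rests on one short line in text extracted from PDF, with no second printing to confirm it.

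Most of this stands, and it sets the severity. It does not remove the defect. Section 5.1.10 tells raters to use the list as printed. Placing a reaction by position is not what the words say, and two raters need not agree on it. The rater training in protocol 5.2 sits under efficacy evaluations and cannot be assumed to cover this scale. The line shows no gap or redaction mark, and the other seven anchors read as complete.

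A reader might infer that the treatment rule in 5.9 is compromised, with edema but no papules falling on either side of 5 at the rater's choice. The documents do not support this, because the grade 5 wording is intact and requires papules. The score is also not the only safeguard. Protocol 5.9 separately stops treatment for a clinically significant adverse event in the judgment of the Principal Investigator or Medical Monitor, and 4.8.6 allows removal for an adverse event that poses unacceptable risk.

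A reader might also infer a copying slip from the cited scale. That scale's text is not in the documents, so the cause cannot be shown.

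**Conclusion.** The concern holds as a minor point. As printed, grade 4 is not a distinct step between grades 3 and 5, grades 2 to 4 are not in order of severity, and erythema with more than minimal edema but no papules has no grade. The consequence is conditional: if raters used this wording, the post-baseline counts at grades 2 to 4 and the mean and median do not reliably reflect ordered severity.

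The size cannot be put as a number, because the documents give no frequency for any dermal grade and do not show the eCRF wording. The effect is limited to descriptive tolerability summaries. The interruption threshold, the adverse-event stopping provisions, the efficacy endpoints, the type I error and the sample size are untouched. The conclusion assumes that the line reads in the source protocol as it does in the text available here.

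**What to change.** 1. Check grade 4 against the cited published scale and correct the line in 5.1.10 so that it is a distinct step between grades 3 and 5. The wording should come from that source and not be guessed.
2. Check which wording the eCRF and source forms carried.
3. Only if it was the printed wording, footnote grades 2 to 4 in Table 14.3.2.2, and caveat the mean and median in Table 14.3.2.1 and in the study report.

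The cost is one line of the scale for later use. For this study, which SAP section 1 records as locked on 09-Sep-2022 and unblinded on 12-Sep-2022, it is a form check and, if needed, notes to two tables and a sentence in the report. No data need to change.
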